#### **4.4. Sponsor Qualified Medical Personnel**

The contact information for the sponsor's appropriately qualified medical personnel for the trial will be documented in the study contact list located in the Investigator Site File. To facilitate access to appropriately-qualified medical personnel on study related medical questions or problems, subjects will be provided with a contact card. The contact card will contain, at a minimum, protocol and investigational compound identifiers, subject study number, contact information for the investigational site and contact details for a help desk in the event that the investigational site staff cannot be reached to provide advice on a medical question or problem originating from another healthcare professional not involved in the subject's participation in the study. The help desk number can also be used by investigational staff if they are seeking advice on medical questions or problems, however it should only be used in the event that the established communication pathways between the investigational site and the study team are not available. It is therefore intended to augment, but not replace the established communication pathways between the investigational site and study team for advice on medical questions or problems that may arise during the study. The help desk number is not intended for use by the subject directly and if a subject calls that number they will be directed back to the investigational site.

## **5. STUDY TREATMENTS**

### **5.1. Allocation to Treatment**

At Visit 1 subjects will be randomized 1:1 to apixaban or usual care (parenteral heparin and/or oral anticoagulation with Vitamin K antagonist (excluding other NOACs)). Treatment

group assignment will be managed using a centralized Internet-based or Interactive Voice Response System (IVRS).

## 5.2. Drug Supplies

### 5.2.1. Formulation and Packaging

Apixaban formulation and packaging details are as follows;

Product	Potency	Primary Packaging	Appearance	Storage
BMS-562247-01 Film Coated Tablet	5 mg	200 tablets per bottle  Open label	Reddish brown, plain, oval shaped, shallow bi-convex film coated tablet	Store at 2- 30°C
BMS-562247-01 Film Coated Tablet	2.5 mg	200 tablets per bottle  Open label	Reddish brown, plain, oval shaped, shallow bi-convex film coated tablet	Store at 2- 30°C

Usual care will be locally sourced, commercial drug supply provided via the investigator site; no packaging or labeling will be performed unless required by local country regulation.

Generally, the sponsor does not intend to cover the cost of usual care in this study. However, the decision to cover the cost of usual care (parenteral heparin and/or oral anticoagulation with Vitamin K antagonist (excluding other NOACs)) in each country will be made by the sponsor based on local requirements and guidelines.

### 5.2.2. Preparation and Dispensing

Sites should refer to the local package inserts for usual care (parenteral heparin and/or oral anticoagulation with Vitamin K antagonist (excluding other NOACs)) treatment for preparation and dispensing information.

Apixaban supplied to the Investigator must be stored in accordance with the clinical label and Investigators Brochure. Apixaban supplies must be stored separately from normal hospital/practice stocks. Until dispensed to the subjects, apixaban will be stored in a securely locked area, only accessible to authorized study personnel.

Usual care (parenteral heparin and/or oral anticoagulation with Vitamin K antagonist (excluding other NOACs)) treatment should be stored in accordance with the local label.

For subjects randomized to apixaban (or to the usual care arm, where usual care medication is stored at study site), the Investigator or delegate should dispense study drug treatment as per label and routine clinical practice, **and visually confirm the subject has received their medicine supply at randomization.**

For subjects randomized to the usual care arm, it is acceptable for the site to provide the subject with a prescription if this medication is not routinely stocked at the site and if this is consistent with routine clinical practice. In these events, visual inspection is ensured by review of the provided prescription.

A treatment log must be completed for either apixaban or usual care as appropriate.

### **5.2.3. Administration**

Apixaban or usual care (parenteral heparin and/or oral anticoagulation with Vitamin K antagonist (excluding other NOACs)) will be administered from randomization up to 30 days following first cardioversion attempt (or 30 days following Visit 2 in the event a subject has spontaneously reverted to normal sinus rhythm before cardioversion) or 90 days post randomization if cardioversion is not performed.

Administration details will be recorded in the case report form (CRF).

Medication errors may result, in this study, from the administration or consumption of the wrong drug, by the wrong subject, at the wrong time, or at the wrong dosage strength. Such medication errors occurring to a study participant are to be captured on the adverse event (AE) page of the CRFs and on the SAE form when appropriate. In the event of medication dosing error, the sponsor should be notified immediately.

Medication errors are reportable irrespective of the presence of an associated AE/SAE, including:

- Medication errors involving subject exposure to the investigational product;
- Potential medication errors or uses outside of what is foreseen in the protocol that do or do not involve the participating subject.

Whether or not the medication error is accompanied by an AE, as determined by the investigator, the medication error and, if applicable, any associated adverse event(s) is captured on an adverse event (AE) CRF page.

#### **5.2.3.1. Usual Care**

Usual care (parenteral heparin and/or oral anticoagulation with Vitamin K antagonist (excluding other NOACs)) will be administered as per local label/practice/guidelines.

The dosing of the Vitamin K antagonist must be individualized according to the subject's sensitivity to the drug as indicated by their INR. INR monitoring should follow the investigators usual practice. All INR values during the study will be recorded in the CRF.

### 5.2.3.2. Apixaban

Apixaban will be administered and dose adjusted as per local label for the prevention of stroke and systemic embolism in subjects with non-valvular AF with provision of additional dosing guidance as detailed below:

If a subject randomized to apixaban is scheduled for an image guided cardioversion strategy, then at least 5 doses of apixaban 5 mg BID should be administered before the procedure is conducted to ensure steady-state exposure.

If the cardioversion must be conducted earlier than 5 doses of apixaban, a single 10 mg loading dose (administered as two 5 mg tablets) followed by 5 mg BID should be administered to achieve immediate steady-state exposure (Japan only: the loading dose is not an available option for those subjects participating in Japan and therefore at least 5 doses of apixaban should be administered before the image guided cardioversion is conducted). The cardioversion should not be performed until at least 2 hours following the loading dose administration.

If a subject meets the criteria for dose reduction, which are at least two of the following characteristics: age  $\geq 80$  years, body weight  $\leq 60$  kg, or serum creatinine  $\geq 1.5$  mg/dl (133 micromole/l) then 2.5 mg BID should be administered for at least 5 doses before cardioversion is conducted or a 5 mg loading dose followed by 2.5 mg BID (Japan only: the loading dose is not an available option for those subjects participating in Japan). Investigators should refer to their local label for dose adjustment guidance for subjects with severe renal impairment. For example the SmPC states "*Patients with exclusive criteria of severe renal impairment (creatinine clearance 15-29 ml/min) should also receive the lower dose of apixaban 2.5 mg twice daily*".

A subject receiving an anticoagulant (oral and/or parenteral)  $\leq 48$  hours prior to screening may be randomized into the study. For subjects randomized to apixaban the transition from an anticoagulant (oral and/or parenteral) is as follows;

- Low molecular weight heparin (LMWH) - apixaban should be started at the time of next scheduled dose and no earlier than 12 hours after the previous parenteral anticoagulation administration. If an image guided cardioversion must be conducted earlier than 5 doses of apixaban, then, as directed above, the loading dose can be utilized.
- Unfractionated Heparin (UFH) - apixaban can be started between 0 to 2 hours after stopping intravenous unfractionated heparin. If an image guided cardioversion must be conducted earlier than 5 doses of apixaban, then, as directed above, the loading dose can be utilized.
- VKA - the VKA should be discontinued and apixaban started when the INR is below 2.0. If image guided cardioversion must be conducted earlier than 5 doses of apixaban, then, as directed above, the loading dose can be utilized. Details of INR will be recorded in the CRF.

- Oral anticoagulant other than a VKA - discontinue the oral anticoagulant being taken and begin apixaban at the next scheduled dose and no earlier than 12 hours after the previous oral anticoagulant administration. If an image guided cardioversion must be conducted earlier than 5 doses of apixaban, then, as directed above, the loading dose can be utilized.

#### **5.2.4. Compliance**

For subjects randomized to apixaban, compliance based on study drug tablet count will be recorded both at the time of cardioversion (Visit 2) and at Visit 3 for all subjects.

For subjects randomized to usual care, compliance is confirmed by ongoing INR monitoring. In addition, tablet count should be recorded both at the time of cardioversion (Visit 2) and at Visit 3 for all subjects where usual care has been dispensed directly by the site.

#### **5.3. Drug Storage and Drug Accountability**

Study drug should be stored in accordance with the label.

Investigators and site staff are reminded to check temperatures as per local practice (ie, manually or by using alarm systems to alert of any excursions) and ensure that thermometers are working correctly as required for proper storage of apixaban. Any temperature excursions should be reported to the sponsor.

Apixaban must be stored as indicated. Deviations from the storage requirements, including any actions taken, must be documented and reported to the sponsor. Once a deviation is identified, apixaban must be quarantined and not used until the sponsor provides documentation of permission to use the product.

#### **5.4. Concomitant Medications**

Physicians should refer to the local package inserts for apixaban and usual care to guide prescribing of concomitant medications. The co-administration of parenteral heparin and apixaban is prohibited.

### **6. STUDY PROCEDURES**

#### **6.1. Visit 1 Enrollment, Screening/Randomization (can occur on the same day)**

##### **6.1.1. Screening Assessments**

The Investigator or designee will:

- Obtain written informed consent.
- Obtain alternate contact.
- Obtain subject demography.
- Obtain relevant medical history.

- Obtain Congestive heart failure, hypertension, age, diabetes, stroke, vascular disease, age, sex category stroke risk score (CHA2DS2-VASc score).
- Assess and record local clinical laboratory parameters.
- Determine if subject meets inclusion/exclusion criteria, including confirmation of heart rhythm status from electrocardiogram (ECG). (ECG taken on the day prior to Visit 1 may be used for this assessment).

### 6.1.2. Randomization Assessments

The Investigator or designee will:

- Randomize subject using a centralized IVRS.
- Dispense study drug treatment as per label and routine clinical practice, and visually confirm the subject has received their medicine supply, see [Section 5.2.2](#).

### 6.2. Visit 2 Cardioversion

The Investigator or designee will:

- Assess and record clinical endpoints (stroke, systemic embolism, major bleeding, clinically relevant non-major bleeding, and all cause death) and whether they meet the serious adverse event reporting criteria.
- Perform study drug treatment compliance check, see [Section 5.2.4](#).
- Assess and record local clinical laboratory parameters, including INR for VKA-treated subjects.
- Assess and record cardioversion details (timing, type, attempts, and rhythm status), and use of image guidance (eg, TEE/TOE or CT).
- Assess and record adverse events.
- Collect and dispense study drug treatment, if required, as per label and routine clinical practice, and visually confirm the subject has received their medicine supply, see [Section 5.2.2](#).

### 6.3. Visit 3 (30 days (±7) Post Cardioversion or 90 days (±7) Following Enrollment Visit 1 if Cardioversion is not Performed). See [Figure 2](#) for Further Examples of Timing of Visit 3.

The Investigator or designee will:

- Assess and record local clinical laboratory parameters, including INR for VKA-treated subjects.

- Assess and record ECG details
- Assess and record clinical endpoints (stroke, systemic embolism, major bleeding, clinically relevant non-major bleeding and all cause death) and whether they meet the serious adverse event reporting criteria.
- Record length of in-hospital stay.
- Assess and record adverse events.
- Collect study drug treatment.
- Perform study drug treatment compliance check, see [Section 5.2.4](#).

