**SCHEDULE OF ACTIVITIES**

The Schedule of Activities table provides an overview of the protocol visits and procedures. Refer to [Study Procedures](#) and [Assessments](#) sections of the protocol for detailed information on each procedure and assessment required for compliance with the protocol.

The investigator may schedule visits (unplanned visits) in addition to those listed on the schedule of activities, in order to conduct evaluations or assessments required to protect the wellbeing of the subject.

Procedure	Visit 1 Enrollment Screening/Randomization a	Visit 2 Cardioversion (or planned cardioversion)	Visit 3 Follow-Up (30 days post cardioversion (Visit 2) or up to 90 days following Visit 1) e
Visit Windows			±7 days
Informed Consent	X		
Obtain Alternative Contact	X		
Inclusion/Exclusion	X		
Demographics	X		
Medical History	X		
CHA 2 DS 2 -VASc score b	X		
Local Laboratory Parameters	X	X	X
Electrocardiogram	X (may be obtained on the day prior to Visit 1)	X	X
Randomization	X		
Cardioversion c		X	
Endpoint Assessments d		X	X
Dispense Study Drug	X	X	
Collect Study Drug		X	X
Study Drug Compliance Check		X	X
Adverse Event Assessment		X	X

a. Screening/Randomization could occur on the same day

b. CHA2DS2-VASc - Congestive heart failure, hypertension, age, diabetes, stroke, vascular disease, age, sex category risk score

c. Cardioversion details (timing, type, attempts, and rhythm status) and use of image guidance

d. Endpoints; stroke, systemic embolism, major bleeding, clinically relevant non-major bleeding, and all cause death

e. See Figure 2 for examples of timing of Visit 3.

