### **3. STUDY DESIGN**

This is a randomized, active controlled, parallel-group, open label study.

[figure not shown]
Approximately 1500 subjects will be randomized 1:1 to apixaban or usual care (parenteral heparin and/or oral anticoagulation with Vitamin K antagonist (excluding other NOACs)). Usual care will be administered as per local practice and/or approved label.

Apixaban or usual care (parenteral heparin and/or oral anticoagulation with Vitamin K antagonist (excluding other novel oral anticoagulants (NOACs))) will be administered from randomization up to 30 days following cardioversion or 90 days post randomization if cardioversion is not performed within that timeframe.

[figure not shown]
Following randomization, clinical endpoints, cardioversion details (timing, type, attempts, and rhythm status), length of in-patient hospital stay and use of image guidance will be collected during the 30 days following the cardioversion or during the 90 days post randomization if cardioversion is not performed.

A schematic diagram below (Figure 1) shows the design of the study:

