#### **6.4. Subject Withdrawal**

Subjects may withdraw from the study at any time at their own request, or they may be withdrawn at any time at the discretion of the investigator or sponsor for safety or behavioral reasons, or the inability of the subject to comply with the protocol-required schedule of study visits or procedures at a given study site.

If a subject does not return for a scheduled visit, every effort should be made to contact the subject. If a subject is lost to follow-up, the enrolling physician (or designee) will attempt to contact the alternate contact.

In any circumstance, every effort should be made to document subject outcome, if possible. The investigator should inquire about the reason for withdrawal, request the subject to return all unused investigational product(s), request the subject to return for a final visit, if applicable, and follow up with the subject regarding any unresolved adverse events (AEs).

If the subject withdraws from the study, and also withdraws consent for disclosure of future information, no further evaluations should be performed, and no additional data should be collected. The sponsor may retain and continue to use any data collected before such withdrawal of consent.

A subject who is withdrawn from the study is expected to be subsequently managed by their physician according to their usual practice. See also [Section 6.7](#).

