#### **7.4.4. Clinically Relevant Non-Major Bleeding**

The definition of clinically relevant non-major bleeding will be clinically overt bleeding that consists of:

- Any bleeding compromising hemodynamics.
- Any bleeding leading to hospitalization.
- Subcutaneous hematoma larger than 25 cm^2, or 100 cm^2 if there was a traumatic cause.
- Intramuscular hematoma documented by ultrasonography.
- Epistaxis that lasted for more than 5 minutes, was repetitive (ie, two or more episodes of bleeding more extensive than spots on a handkerchief within 24 hours), or led to an intervention (eg, packing or electrocoagulation).
- Gingival bleeding occurring spontaneously (ie, unrelated to eating or tooth brushing) or lasting for more than 5 minutes.
- Hematuria that was macroscopic and was spontaneous or lasted for more than 24 hours after instrumentation (eg, catheter placement or surgery) of the urogenital tract.
- Macroscopic gastrointestinal hemorrhage, including at least one episode of melena or hematemesis, if clinically apparent with positive results on a fecal occult-blood test.
- Rectal blood loss, if more than a few spots on toilet paper.
- Hemoptysis, if more than a few speckles in the sputum and not occurring within the context of pulmonary embolism or:
  - Any other bleeding type considered to have clinical consequences for a subject, such as medical intervention, the need for unscheduled contact (visit or telephone call) with a physician, or temporary cessation of a study drug; or
  - Associated with pain or impairment of activities of daily life.

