## **8. ADVERSE EVENTS**

In this clinical protocol adverse and serious adverse event reporting will be managed according to the following BMS standard operating definitions and procedures.

An *Adverse Event (AE)* is defined as any new untoward medical occurrence or worsening of a preexisting medical condition in a clinical investigation subject administered study drug and that does not necessarily have a causal relationship with this treatment. An AE can therefore be any unfavorable and unintended sign (such as an abnormal laboratory finding), symptom, or disease temporally associated with the use of study drug, whether or not considered related to the study drug.

The causal relationship to study drug is determined by a physician and should be used to assess all adverse events (AE). The causal relationship can be one of the following:

- Related: There is a reasonable causal relationship between study drug administration and the AE.
- Not related: There is not a reasonable causal relationship between study drug administration and the AE.

The term "reasonable causal relationship" means there is evidence to suggest a causal relationship.

Adverse events can be spontaneously reported or elicited during open-ended questioning, examination, or evaluation of a subject. (In order to prevent reporting bias, subjects should not be questioned regarding the specific occurrence of one or more AEs).

BMS will be reporting adverse events to regulatory authorities and ethics committees according to local applicable laws including European Directive 2001/20/EC and Food and Drug Administration (FDA) Code of Federal Regulations 21 CFR Parts 312 and 320.

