### **8.1.1. Serious Adverse Event Collection and Reporting**

Sections 5.6.1 and 5.6.2 in the Investigator Brochure (IB) represent the Reference Safety Information to determine expectedness of serious adverse events for expedited reporting.

Following the subject's written consent to participate in the study, all SAEs, whether related or not related to study drug, must be collected, including those thought to be associated with protocol-specified procedures. All SAEs must be collected that occur during the screening period and within 30 days of discontinuation of dosing.

The investigator should report any SAE that occurs after these time periods and that is believed to be related to study drug or protocol-specified procedure.

An SAE report must be completed for any event where doubt exists regarding its seriousness.

If the investigator believes that an SAE is not related to study drug, but is potentially related to the conditions of the study (such as withdrawal of previous therapy or a complication of a study procedure), the relationship must be specified in the narrative section of the SAE Report Form.

SAEs, whether related or not related to study drug, and pregnancies must be reported to BMS (or designee) within 24 hours of awareness of the event. SAEs must be recorded on the SAE Report Form; pregnancies on a Pregnancy Surveillance Form (electronic or paper forms). The preferred method for SAE data reporting collection is through the electronic case report form (eCRF). The paper SAE/pregnancy surveillance forms are only intended as a back-up option when the eCRF system is not functioning. In this case, the paper forms are to be transmitted via email or confirmed facsimile (fax) transmission to:

**SAE Email Address:** Refer to [Contact Information list](#).

**SAE Facsimile Number:** Refer to Contact Information list.

For studies capturing SAEs through electronic data capture (EDC), electronic submission is the required method for reporting. In the event the electronic system is unavailable for transmission, paper forms must be used and submitted immediately. When paper forms are used, the original paper forms are to remain on site.

**SAE Telephone Contact** (required for SAE and pregnancy reporting): Refer to Contact Information list.

If only limited information is initially available, follow-up reports are required. (Note: Follow-up SAE reports must include the same investigator term(s) initially reported).

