### **8.2.1. Nonserious Adverse Event Collection and Reporting**

The collection of nonserious AE information should begin at initiation of study drug. Nonserious AE information should also be collected from the start of a placebo lead-in period or other observational period intended to establish a baseline status for the subjects.

Nonserious AEs should be followed to resolution or stabilization, or reported as SAEs if they become serious (see [Section 8.1.1](#)). Follow-up is also required for nonserious AEs that cause interruption or discontinuation of study drug and for those present at the end of study treatment as appropriate. All identified nonserious AEs must be recorded and described on the nonserious AE page of the CRF (paper or electronic).

Completion of supplemental CRFs may be requested for AEs and/or laboratory abnormalities that are reported/identified during the course of the study.

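### Visit 3 may fall up to 7 days before the stated 30-day (90-day) endpoint window ends, with no later contact scheduled; a -0/+7 window or a short call would close this small gap

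*Protocol*

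**What the plan says.** Protocol Section 3 defines the observation window: clinical endpoints "will be collected during the 30 days following the cardioversion or during the 90 days post randomization" where there is no cardioversion. Treatment runs for the same length of time (Section 5.2.3).

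Endpoint assessments are scheduled only at Visits 2 and 3. The Schedule of Activities labels the latter "Follow-Up (30 days post cardioversion (Visit 2) or up to 90 days following Visit 1" and allows 7 days either side; Section 6.3 repeats this as "30 days (±7) Post Cardioversion or 90 days (±7) Following Enrollment Visit 1". Study drug is collected at that visit. No visit or call follows it, and outside the EU it is the end of trial (Section 13.2). Section 6.3 points to Figure 2 for timing examples; that figure is not visible in the text available to us.

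Three other provisions bear on what happens after Visit 3:

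- Section 8.1.1: "All SAEs must be collected that occur during the screening period and within 30 days of discontinuation of dosing". Section 8 adds: "Adverse events can be spontaneously reported or elicited during open-ended questioning, examination, or evaluation of a subject".
- Section 8.2.1: "The collection of nonserious AE information should begin at initiation of study drug". It gives no end date.
- Section 6.4: "If a subject does not return for a scheduled visit, every effort should be made to contact the subject". This concerns missed visits, loss to follow-up and withdrawal.

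SAP 8.2.4 analyses stroke, embolism and death by intention to treat. It counts bleeding only while subjects are on treatment, in the safety set. SAP 8.1.3 and 8.2.4 report event proportions with exact 95% intervals and exact risk ratios. The SAP sets no day-30 or day-90 cut-off and no censoring rule for the clinical endpoints.

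**The concern.** The visit tolerance is symmetric, but the endpoint window has a fixed end. A subject seen on day 23 is fully compliant, yet nobody is scheduled to ask about days 24 to 30. The outreach in Section 6.4 is not triggered, because that subject has missed nothing.

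Two consequences follow. For stroke, embolism and death, the rest of the window depends on someone reporting the event. For bleeding, drug handed in early may end the treatment period early, so the period in which bleeds are counted can fall short of the 30 days that the design describes.

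The main output of a descriptive study is its event counts. Kaplan-Meier estimates and hazard ratios are little affected if subjects are censored at last contact. Simple proportions and risk ratios cannot adjust for a shortened window, and with so few events predicted, one unrecorded stroke would show.

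**Working it through.** **Inputs.** Visit 3 tolerance: 7 days either side (Section 6.3, Schedule of Activities). Window: 30 or 90 days (Section 3). Predicted stroke or systemic embolism within 30 days after cardioversion: 1 + 3 = 4 events in 1500 subjects (Section 9.1). The documents give no distribution of visit dates, no hazard shape and no rate of capture through serious event reporting, so these are assumed.

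**The plan's own figures.** 4/1500 = 0.27%, stated as about 0.3%. 480/0.01 = 48,000, as stated. Both reproduce, and neither is in dispute.

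**Earliest compliant visit.** 30 - 7 = day 23; 90 - 7 = day 83.

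**Share of the 30-day window after Visit 3, constant hazard (assumption).**

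- Every visit on day 23: 7/30 = 23.3%; 4 × 0.2333 = 0.93 events. This is a ceiling.
- Visit dates uniform over days 23 to 37 (assumption): half the subjects come early, by 3.5 days on average, so the mean gap is 0.5 × 3.5 = 1.75 days. 1.75/30 = 5.8%; 4 × 0.0583 = 0.23 events. Counting whole days instead gives 28/15 = 1.87 days, 6.2% and 0.25 events.

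**Risk concentrated early (assumption: hazard halves every 10 days).** With k = ln2/10, the share of 30-day risk after day d is f(d) = (exp(-kd) - exp(-30k)) / (1 - exp(-30k)).

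- f(23) = (0.2031 - 0.1250)/0.8750 = 8.9%; 4 × 0.0892 = 0.36 events.
- Uniform visits: the integral of f from 23 to 30, divided by 14, is 2.1%; 4 × 0.0205 = 0.08 events.

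**After capture through serious event reporting (assumption: 50% to 90%), constant hazard.**

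| Visit dates | Before capture | 50% captured | 90% captured |
|---|---|---|---|
| Uniform | 0.23 | 0.12 | 0.02 |
| All on day 23 | 0.93 | 0.47 | 0.09 |

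**No cardioversion.** 7/90 = 7.8% at most; 1.75/90 = 1.9% with uniform visits.

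**Reach of the reporting duty.** If dosing ends at Visit 3, it runs to day 23 + 30 = 53, or day 83 + 30 = 113. Both lie beyond the endpoint window.

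**Bleeding.** No loss is calculated. If treatment stops at an early Visit 3, later bleeds lie outside the SAP's analysis period, so the period is shorter rather than under-observed. The documents predict no rate for clinically relevant non-major bleeding.

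**The case against.** A symmetric tolerance around a nominal day is ordinary scheduling practice, and the protocol describes itself as pragmatic. The events that matter most are covered: death is always a serious adverse event, a stroke or proven embolism normally is one, and their collection is mandatory well past day 30. Unplanned visits are allowed. The 23% figure needs every subject to come on the earliest permitted day, which nothing in the documents suggests. There are no hypothesis tests or decision rules to upset.

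Most of this stands, and it is why the point is minor. What remains is narrow: the reporting duty has no contact attached to it, so the stated window is not actively checked to its end in subjects seen early.

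A reader might infer that nonserious endpoint events are being lost, since Section 7.4.4 counts events as mild as "Rectal blood loss, if more than a few spots on toilet paper" and Section 8.2.1 sets no end to nonserious collection. The documents do not support that as a loss to the analysis. The SAP counts bleeding during treatment and drug is collected at Visit 3, so a later bleed would count only if treatment continued after that visit, which the protocol does not plan.

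A reader might also infer bias between arms. The window is the same in both, and nothing indicates that visit timing would differ by arm.

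**Conclusion.** The point holds as a minor, inexpensive improvement. The written rule lets the last scheduled assessment precede the end of the stated window by up to 7 days. For those subjects, the remainder of the window for stroke, embolism and death rests on serious event reporting without a scheduled contact, and the period in which bleeding is counted may be shortened.

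The expected effect is a fraction of one event: about 0.23 of 4 under constant hazard and uniform visit dates, and less if risk is concentrated early or serious event reporting works well. All three of those conditions are assumptions. The ceiling of 0.93 events describes an implausible visit pattern and should not be read as the expected loss.

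The tolerance is also a smaller source of unequal follow-up than the free timing of cardioversion. Figure 2 could add guidance on timing that we cannot see, but the written window is clear without it.

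**What to change.** 1. In Protocol 6.3 and the Schedule of Activities, set the Visit 3 window to -0/+7 days. Alternatively, keep the present window and require a brief telephone call or record check of endpoint status on or after day 30 after cardioversion (day 90 after randomization if none) whenever Visit 3 is earlier.
2. As a companion change in SAP 8.2.4, count post-cardioversion stroke, embolism and death to day 30 (day 90 if no cardioversion), censoring there or at last contact if earlier in time-to-event analyses. The simple proportions then refer to a common window. This recovers no missed event on its own, and it does not equalise the SAP's 'ALL' period, whose length varies with the timing of cardioversion.

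The cost is slightly less scheduling flexibility under -0/+7, or one short contact for each subject seen early. Under -0/+7 the end-of-study anticoagulant transition (Section 6.7) must be planned for visits after day 30, as visits up to day 37 already require. The SAP change is wording only.
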